#### **Study sample and setting**

The study will be conducted at the Helsinki University Hospital; more specifically at the operating department K of the Peijas Hospital. The study population consist of adult female and male patients scheduled for either total hip arthroplasty (THA) or total knee arthroplasty (TKA). A control group and an experimental (intervention) group will be formed. The participants are recruited at their preoperative visits to the outpatient clinic two to three weeks prior to their scheduled operations. The inclusion criteria: 18 years of age or older, able to comprehend the study information and complete the questionnaires, and operation being performed under spinal anesthesia. One exclusion criterion for the intervention group is that the planned surgery is performed on Friday, because the postoperative visits cannot be performed during the weekend.

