## **Randomization and sample size**

Randomization of participants is performed by independent third parties (two nurse assistants at the outpatient clinic). All patients scheduled for THA and TKA attending the outpatient clinic are considered eligible and invited to participate in randomization if they meet the inclusion criteria. Eligible patients will draw one of two cards; one indicate an invitation to participate the study and the other is blank, indicating no participation in the study. Patients in the control group will be recruited every other week and patients for the intervention group every week between. This pattern will be repeated until the desired number of patients are recruited. This stratification will ensure that patients in different groups do not exchange information in the postoperative ward. The sample size requirement for comparing two means was checked with power analysis (2-sided test) with  $\alpha = 0.05$ ,  $\beta = 0.9$ , standard deviation 0.08, and differences of means 0.03 in 15D scores, which is within the slight difference of 0.015-0.035 (Alanne, Roine, Räsänen, Vainiola, & Sintonen, 2015). A sufficient sample size is determined to be 152 per group.

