## **Intervention**

Traditionally during the intra- and postoperative phases of surgical care, the patient is cared for by several nurses; i.e. by an anesthetic nurse in the operating room and by a recovery room nurse in the Post Anesthesia Care Unit (PACU). Furthermore, the pre- and postoperative visits to the surgical patients are rare in Finland; mainly due to resources and new surgical processes where patients arrive to the hospital in the morning of the scheduled procedure.

The new perioperative practice model denotes that the one and same nurse will meet the patient at his/her arrival to the operating department, and will care for the patient both in the operating room and in the PACU. Thus, the nursing care in the operating room and in the PACU remains the same but will be organized in a new way which focuses on the patient centered individual care and the continuity of care. Furthermore, the same nurse will visit the patient at the surgical unit on the first postoperative day.

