## **Data collection and Outcome Measures**

The demographic data of the participants includes age, gender, diagnosis, procedure, and ASA class (ASA Physical Status Classification 2014). Further patient data will be collected by 1) The Good Perioperative Nursing Care Scale (Leinonen & Leino-Kilpi 2001) measuring the quality of perioperative care; 2) 15D instrument measuring the health-related quality of life among adults (Sintonen 2001) and 3) STAI, the State-Trait Anxiety Inventory; measuring anxiety in adults (Spielberger et al. 2010). The schedule for patient data collection is presented in Table 1.

**Table 1.** Schedule of patient data collection

Instrument	Baseline (preoperative visit 2-3 weeks prior to surgery)	Cross-section (at discharge)	Post-test (three months after discharge)
15 D	x		x
STAI	x		x

Good Perioperative Nursing Care Scale		x	
---------------------------------------	--	---	--

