### **Secondary Outcome Measures**

1. Change from baseline Surgery-related anxiety at three months after the surgical procedure. Time frame: Baseline 2-3 weeks prior to, and post-measurement 3 months after the procedure (The State-Trait Anxiety Inventory (STAI))
2. Quality of perioperative care as experienced by surgical patients. Time frame: On average the third postoperative day, depending the time of discharge (Good Perioperative Nursing Care Scale)

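### Alternating the groups by recruitment week does not ensure that they are apart on the postoperative ward, because surgery follows two to three weeks later

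*Combined protocol and SAP*

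**What the plan says.** Under Randomization and sample size, the card draw decides whether a patient takes part, and the calendar decides the group: "Patients in the control group will be recruited every other week and patients for the intervention group every week between". The only reason given for alternating weeks follows: "This stratification will ensure that patients in different groups do not exchange information in the postoperative ward".

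Study sample and setting fixes when recruitment happens: "The participants are recruited at their preoperative visits to the outpatient clinic two to three weeks prior to their scheduled operations". Table 1 (Data collection and Outcome Measures) gives the same interval for the baseline measurement.

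The Intervention section describes current practice, in which "patients arrive to the hospital in the morning of the scheduled procedure". It places one part of the new model on the ward: "the same nurse will visit the patient at the surgical unit on the first postoperative day". The timing of the care-quality scale is given under Secondary Outcome Measures: "On average the third postoperative day, depending the time of discharge". Friday surgery is an exclusion for the intervention group only (Study sample and setting).

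**The concern.** The alternation is keyed to the recruitment week, but the property claimed for it concerns the postoperative ward. Patients reach the ward according to their surgery date, which lies two to three weeks after recruitment and varies by a full week. Unless something carries the recruitment-week pattern over to surgery weeks, the two groups can be on the ward together.

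Ward separation is the plan's only stated justification for assigning group by calendar week. The outcome most exposed is the Good Perioperative Nursing Care Scale: it is completed at discharge, after the day-1 nurse visit on the surgical unit. A control who hears of that visit before rating their own care might rate it differently. A reader who relies on the plan's wording would rule this out without grounds.

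**Working it through.** The plan gives no figure for ward overlap, and its sample size of 152 per group plays no part here. The check is a calendar count.

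**Inputs from the protocol**
- Alternation period: 7 days (Randomization and sample size).
- Interval from recruitment to surgery: 14 to 21 days (Study sample and setting; Table 1).
- No Friday surgery in the intervention group (Study sample and setting).
- Discharge on average on the third postoperative day, variable (Secondary Outcome Measures).

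**Step 1. Can both groups have surgery in the same week?** Call the Monday of week k day 0, with week k a control week.
- Control seen on day 0, interval 21 days: surgery on day 0 + 21 = 21.
- Intervention patient seen on day 7 (week k+1), interval 14 days: surgery on day 7 + 14 = 21.

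Both have surgery on the Monday of week k+3. The next pair of weeks behaves the same way: an intervention patient at 7 + 21 = 28 and a control at 14 + 14 = 28. The spread of the interval, 21 − 14 = 7 days, equals the alternation period, so any two adjacent recruitment weeks can meet. This step uses only the plan's own range.

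**Step 2. When would surgery weeks alternate?** They do so if all patients recruited in one week have surgery in one and the same later week. Two examples are a single interval for everyone (all 14 or all 21 days), or Monday clinics only with intervals of 14 to 18 days (Monday to Friday of week k+2). The documents state no such rule, and no gap week or separate ward area.

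**Step 3. Overlap that remains even with one fixed interval.** Assume surgery Monday to Friday for controls and Monday to Thursday for intervention, count surgery days as slots, and count the discharge day as a ward day.
- Discharge on day 2: no overlap.
- Discharge on day 3: a Friday control leaves on Monday and can meet a Monday intervention patient. This involves 1 of 5 control slots (20%) and 1 of 4 intervention slots (25%).
- Discharge on day 4: control slots on Monday, Thursday and Friday (3 of 5, 60%) and intervention slots on Monday, Tuesday and Thursday (3 of 4, 75%).

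**Step 4. Illustration with a spread interval.** Assume clinic visits Monday to Friday and intervals spread evenly over 14 to 21 days; neither is in the documents. Counting possible weekday surgery slots by visit day, Monday to Friday:
- Control, two weeks after the recruitment week: 5+4+3+2+1 = 15; three weeks after: 1+2+3+4+5 = 15.
- Intervention (no Fridays), two weeks after: 4+3+2+1+0 = 10; three weeks after: 1+2+3+4+4 = 14.

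So 15 of 30 control slots (50%) and 14 of 24 intervention slots (58%) fall in a week that also holds the other group's two-week slots. Under Step 2 the corresponding figure is 0%. These are calendar slots, not patients and not contacts. The documents do not say where the trial lies between the two.

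**The case against.** The strongest reply is that this is a fault in one sentence of rationale with little consequence. The new model is a way of organising nursing care on arrival, in the operating room and in the PACU, and talk on the ward cannot deliver that care to a control. Only the day-1 visit takes place on the surgical unit, and only one secondary scale is completed soon afterwards. No analysis and no sample-size figure rests on the claim. Full separation was also never available: patients who draw the blank card are on the ward too, presumably under usual care, so only contact between enrolled patients is at stake. All of this stands and limits the importance of the point.

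It does not rescue the claim. The protocol asserts a guarantee, and its own stated interval contradicts that guarantee.

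A reader might go further and infer that most weeks were mixed, that contamination took place, or that the primary result is biased. The documents support none of these. Any percentage of mixed weeks needs an assumed interval distribution, clinic days and recruitment rate, and a shared surgery week is not the same as contact on the ward. The 15D is measured before surgery and at three months, and nothing in the plan shows that ward contact would move it. The Friday exclusion in one group only is a separate matter; here it enters only the slot counts.

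**Conclusion.** The point holds in a limited form. Alternating by recruitment week, with a two-to-three-week interval to surgery, does not have the property the protocol claims for it. This follows from the stated interval and alternation period alone.

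The amount of ward overlap cannot be determined from the documents. It could be confined to stays across a weekend, if one interval applied to everyone, or it could extend to every surgery week. The 0% to 50% (control) and 58% (intervention) slot figures rest on assumed schedules and only show how far the answer depends on them. The possible consequence is contamination of the care-quality scale at discharge, of unknown size and direction. No effect on the primary 15D change is shown. The wording should be fixed because the correction is cheap; the point does not by itself undermine the trial.

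**What to change.** Define the alternating week by the calendar week of the scheduled surgery date, and state that this date is set before enrolment and independently of it. The text should also say that this reduces overlap but does not exclude it for longer stays or on discharge days; the slot counts for one fixed interval apply equally to this rule.

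The cost is protocol wording and reading the group from the surgery calendar, with no extra visits. There are three downsides:
- Surgery scheduling becomes a possible route for selection. The calendar is already predictable under the current rule, so the added risk is modest.
- One clinic week may yield patients for both groups, so staff need both sets of materials.
- Some patients will be rescheduled into the other group's week.

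If allocation is not changed, replace 'will ensure' with a statement that the groups may overlap on the ward, and report possible contamination of the discharge care-quality scale as a limitation. Recording surgery and discharge dates would allow the actual overlap to be counted.

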## **Intervention**

Traditionally during the intra- and postoperative phases of surgical care, the patient is cared for by several nurses; i.e. by an anesthetic nurse in the operating room and by a recovery room nurse in the Post Anesthesia Care Unit (PACU). Furthermore, the pre- and postoperative visits to the surgical patients are rare in Finland; mainly due to resources and new surgical processes where patients arrive to the hospital in the morning of the scheduled procedure.

The new perioperative practice model denotes that the one and same nurse will meet the patient at his/her arrival to the operating department, and will care for the patient both in the operating room and in the PACU. Thus, the nursing care in the operating room and in the PACU remains the same but will be organized in a new way which focuses on the patient centered individual care and the continuity of care. Furthermore, the same nurse will visit the patient at the surgical unit on the first postoperative day.

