**Statistical Analysis Plan:**

Descriptive statistics will be used to present characteristics of the study participants. One- and multi-way analysis of variance will be used to compare means of groups. Interaction terms will be used to compare means of the groups defined by combinations of categorical independents. Tukey's adjustment will be used to account for multiple comparison if necessary. Statistical significance of dependencies between categorical variables are tested using Chi-square tests. SAS® statistical software, version 9.4 (SAS Institute Inc., Cary, NC, USA) will be used in statistical analysis.

In the analysis of the patient data, collected with the GPNCS, if a respondent answers to less than 50% of the quality statements, his or her response will be excluded from the analysis. Frequencies and percentages obtained with the Pearson chi-square test are calculated for the background data. Non-parametric tests are used when comparing background factors with quality categories. The reliability of the scale is checked with a Cronbach's alpha coefficient. In the analysis of data sets, the non-parametric tests will include the Kruskall-Wallis test and Mann Whitney U-test with Bonferroni corrections. A *p*-value of 0.05 is considered statistically significant.

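### Patients share nurses, most strongly in the intervention arm, but the SAP's tests treat patients as independent and the treating nurse is not among the listed data

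*Combined protocol and SAP*

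**What the plan says.** The protocol's Intervention section describes usual care as care in which "the patient is cared for by several nurses": one in the operating room and another in the PACU. Under the new model "the one and same nurse will meet the patient at his/her arrival to the operating department" and then cares for that patient in both places. In addition, "the same nurse will visit the patient at the surgical unit on the first postoperative day".

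The section on randomization and sample size compares two means, with "standard deviation 0.08, and differences of means 0.03 in 15D scores", and concludes: "A sufficient sample size is determined to be 152 per group". It mentions no design effect.

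For the arm comparison the SAP states: "One- and multi-way analysis of variance will be used to compare means of groups". Its paragraph on the Good Perioperative Nursing Care Scale adds Kruskal-Wallis and Mann-Whitney tests. It names no nurse term, random effect or cluster-robust standard error. The patient data listed under Data collection and Outcome Measures are age, gender, diagnosis, procedure, ASA class and the three questionnaires; the treating nurse is not listed.

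The documents do not give the number of nurses, the number of patients per nurse, an ICC, or whether the nurses who deliver the new model also treat control patients.

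**The concern.** Unless there are as many nurses as patients, several patients will share a nurse, and their outcomes may be correlated. The sharing is strongest in the intervention arm, where a single nurse accounts for the whole perioperative contact. In the control arm it is spread over two nurses per patient.

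ANOVA and the rank tests have no place for this correlation. If nurse effects do not cancel between the arms, confidence intervals are too narrow and p-values too small. A difference produced by a few well-liked nurses could then be read as an effect of the care model. The outcome most exposed is the secondary one that asks patients to rate the care: "Quality of perioperative care as experienced by surgical patients". If the nurse is not recorded, nobody can check or repair this after the trial.

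Allocation by alternating recruitment week is a separate source of dependence, and a week term does not remove the nurse effect.

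**Working it through.** **Inputs from the protocol.** Two-sided alpha 0.05; 90% power (printed as beta = 0.9); SD 0.08; difference 0.03; 152 per group.

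**Assumptions, not in the documents.** Number of nurses K = 5, 10 or 20; within-nurse ICC ρ = 0.01, 0.05 or 0.10; equal numbers of patients per nurse unless stated.

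**Step 1: the plan's own figure.** n = 2 × [(1.960 + 1.282) × 0.08 / 0.03]² = 149.4, so 150 per group; the t-test version gives 151. The stated 152 is reproduced closely, on the basis of independent patients. Power at 152 is 90.5% (normal approximation).

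**Step 2: nurse effects in the intervention arm only.**
- Design effect in that arm: DE = 1 + (152/K − 1)ρ
- True SE / ANOVA SE: f = √[(1 + DE)/2]
- Type I error: 2 × [1 − Φ(1.96/f)]
- Power for 15D, using the true SE: Φ(0.03 / (0.08 × √[(1 + DE)/152]) − 1.96)

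Example, K = 10 and ρ = 0.05: DE = 1 + 14.2 × 0.05 = 1.71; f = √1.355 = 1.164; type I error 9.2%; power 80.2%.

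| K | ρ | f | Type I error | Power (15D) |
|---|---|---|---|---|
| 20 | 0.01 | 1.02 | 5.4% | 89.6% |
| 20 | 0.05 | 1.08 | 6.9% | 85.7% |
| 20 | 0.10 | 1.15 | 8.9% | 80.9% |
| 10 | 0.01 | 1.04 | 5.8% | 88.5% |
| 10 | 0.05 | 1.16 | 9.2% | 80.2% |
| 10 | 0.10 | 1.31 | 13.4% | 70.5% |
| 5 | 0.01 | 1.07 | 6.7% | 86.3% |
| 5 | 0.05 | 1.32 | 13.7% | 69.9% |
| 5 | 0.10 | 1.57 | 21.2% | 54.8% |

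The true SE is thus 2% to 57% larger than ANOVA reports. Expressed as understatement of the ANOVA SE, this is 1 − 1/1.016 = 2% to 1 − 1/1.57 = 36%. Simulation agrees with the formula: 8.9% at K = 10, ρ = 0.05 and 20.9% at K = 5, ρ = 0.10.

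**Step 3: same nurses in both arms, balanced workloads, same effect in each arm.** The nurse effect cancels from the difference but stays in the ANOVA residual, so f = √(1 − ρ). For ρ = 0.01, 0.05 and 0.10, f is 0.995, 0.975 and 0.949, and the type I error is 4.9%, 4.4% and 3.9%. The test is then about right or slightly conservative. Letting each control patient's nurse effect be the average of two nurses from the same pool gives the same picture in simulation (4.4% to 4.7%).

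**Step 4: other rosters, simulated at K = 10, ρ = 0.05.**
- Wholly separate nurse pools for the two arms: about 11% to 13%, depending on how the two control nurses are modelled.
- Control operating-room nurses from the intervention pool, recovery nurses from another, each contributing half: about 7%.
- Shared pool with uneven workloads: about 9%.

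**The case against.** The strongest objection is that the control arm is not free of nurse clustering. Each control patient has an anesthetic nurse and a recovery room nurse, and those nurses also treat other study patients. Both arms run in one operating department in alternating weeks, and the protocol says the content of nursing care is unchanged and only its organization differs. If one pool of nurses serves both arms, nurse effects largely cancel, and Step 3 shows that ANOVA is then slightly conservative.

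This stands, and it limits the point. A reader might infer that the correlation exists only in the intervention arm and that the standard errors are certainly too small. The documents support neither: the roster decides the direction of the error as well as its size. Step 2 is one scenario, not a description of the trial.

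The objection does not remove the point. Cancellation needs a shared pool, balanced workloads and similar nurse effects under both models of care. The protocol promises none of these. Usual care splits the patient between two nursing roles, and the Background says the pilot of the new model used an anesthesia nurse throughout. Recovery nurses may therefore fall outside the intervention pool, although the protocol does not say so for this trial. With partial overlap or uneven workloads the error rate is still inflated (Step 4).

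It is also fair to say that every size given here rests on assumed nurse numbers and ICCs, and that with many nurses and a small ICC the effect is minor.

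**Conclusion.** The point holds in conditional form. The planned tests ignore a dependence that the intervention itself strengthens, and the listed data would not allow it to be examined. The standard error of the arm difference is too small unless the same nurses serve both arms with balanced workloads and similar effects.

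Across the assumed range, the type I error of the nominal 5% test runs from about 4% to 5% (shared, balanced roster) to between 5.4% and 21% (nurse effects in the intervention arm only). It can be higher still if the arms use separate nurse pools. The figure of 57% is how much larger the true standard error is; it should not be read as the amount by which ANOVA understates it, which is at most 36% in the same range.

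The effect is probably small for the primary outcome, 15D at three months: at ICC 0.01 the type I error is 5.4% to 6.7%. It is probably larger for the care-quality score, which rates the nursing at discharge. A reader might take that ordering as shown, but it is a reasoned expectation that no figure in the documents demonstrates.

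**What to change.** 1. Record a coded nurse identifier for every patient in both arms: the single nurse for intervention patients, and the operating-room and PACU nurses for controls.
2. State in the protocol how many nurses take part and how far they overlap between arms.
3. For the arm comparisons of 15D, STAI and the care-quality score, replace ANOVA and the rank tests with a mixed model that has a random nurse effect covering both arms. It should be crossed or multiple-membership where nurses overlap, allow variance to differ by arm, and use small-sample degrees of freedom such as Kenward-Roger. This is in addition to whatever term handles recruitment week.
4. Report the nurse ICC and the number of patients per nurse.

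A nurse effect fitted in the intervention arm only would not be adequate. It would miss clustering among controls and, with a shared roster, would ignore the covariance between arms and cost power. Recording nurses in one arm only would also leave the overlap unknown.

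The cost is a nurse-code field in the data form (two entries for a control patient) and a change of SAP wording. The model can be fitted in SAS, the software already named. The downside is probably somewhat wider confidence intervals. No extra patients or staff are needed for the change of analysis itself.
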